12.2 Sample Size Considerations

The power analysis is based on the primary aim of comparison of serum antibody, specificity, memory B cell derived polyclonal antibodies (MpAb) and HA-specific CD4 T cell counts (in log scale to stabilize variance) between the group of subjects vaccinated with egg derived TIV IM and the group of subjects vaccinated with Baculovirus derived TIV IM. In this explorative study, the HA-specific CD4 T cell response to the Baculovirus derived vaccine is unknown and thus no information is available about the group difference. But our past experience indicated the coefficient of variation (CV) of HA-specific CD4 T cell counts varied between 0.25 and 0.4 [18]. If we assume CV and use percent-change differences in HA-specific CD4 T cell counts relative to the group with egg derived vaccine, with 45 subjects per group, we will have 80% power to detect at least 10% ~ 20% difference in HA-specific CD4 T cell counts between the two groups. This power analysis is based on two-sample t test with a two-sided significance level of 0.05 and equal allocation of subjects to any two groups.

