12.4 Final Analysis Plan

We will define the groups as: G1 (egg derived vaccine) = G1a (seronegative to pH1N1 virus and receiving egg derived vaccine) + G1b (seropositive and receiving egg derived vaccine); G2 (baculovirus derived vaccine) = G2a (seronegative to to pH1N1 virus and receiving baculovirus derived vaccine) + G2b (seropositive and receiving baculovirus derived vaccine). The log transformation will be applied to stabilize variance, as suggested by our past experience [18]. The between-group and among-group comparison in each of the outcomes will be based on both standard statistical analysis approaches using summary statistics and the complicated random variance model approach. Specifically, each of CD4 specific cells for different Influenza proteins (eg HA, NP etc), memory B cell derived polyclonal antibodies, HAI and MN titers among the four groups and between G1 and G2, between G1a and G2a, and between G1b and G2b, we will use maximum responses or maximum boost responses (maximum value after day 0 – value at day 0) or maximum fold increase as endpoint and do group comparison by ANOVA for among-group comparison and two-sample t-test for between-group comparison, or their nonparametric analogy of Kruskal-Wallis test and Wilcoxon Rank sum test, respectively, may also be applied for robustness. Multiple comparisons may subject to Bonferroni correction, if appropriate. Correlation test such as Pearson correlation analysis, or its nonparametric analogy of Spearman correlation analysis, will be used to study how baseline CD4 responses and/or memory B cell derived polyclonal antibodies, HAI, MN titers affect the boost responses of CD4, memory B cell derived polyclonal antibodies, HAI and MN titers after vaccination.

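### Section 12.2: 45 per group does not give 80% power for a 10% difference at any CV the protocol states; power there is at most 52%

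*Combined protocol and SAP*

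**What the plan says.** Section 12.2 (Sample Size Considerations) compares the egg-derived and baculovirus-derived vaccine groups on HA-specific CD4 T cell counts, taken on the log scale. It reports from past experience that "the coefficient of variation (CV) of HA-specific CD4 T cell counts varied between 0.25 and 0.4". It proposes to "use percent-change differences in HA-specific CD4 T cell counts relative to the group with egg derived vaccine" and concludes that "with 45 subjects per group, we will have 80% power to detect at least 10% ~ 20% difference in HA-specific CD4 T cell counts". The test is a "two-sample t test with a two-sided significance level of 0.05 and equal allocation of subjects to any two groups".

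Section 12.4 (Final Analysis Plan) keeps the log scale: "The log transformation will be applied to stabilize variance, as suggested by our past experience".

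Three things are left open: the direction of the difference, how the CV becomes a standard deviation, and which CV belongs with which end of the 10% to 20% range.

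**The concern.** The section supplies every input needed to check its claim (sample size, test, alpha, CV range and effect size), and a 10% difference looks too small for 45 per group. At CV 0.25, a 10% shift is only about 0.4 of a standard deviation. A two-sample t test with 45 per group needs about 0.6 for 80% power.

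This sentence is the only numerical support given for 45 per group, and it is tied to the primary aim. A reader who takes it at face value expects to miss a true 10% difference one time in five. If the real figure is one in two or worse, a null result could be read as ruling out modest differences that the comparison had little chance of finding.

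**Working it through.** **Inputs, all from section 12.2:** n = 45 per group, equal allocation, two-sample t test, two-sided alpha 0.05, target power 80%, CV 0.25 to 0.4, difference 10% to 20% relative to the egg-derived group.

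**Step 1. Required standardised difference.** Solving the noncentral t power function with n = 45 per group (88 degrees of freedom) for 80% power gives d = 0.597.

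**Step 2. Standardised effect under three readings.** The text fixes neither scale nor direction, so all three are shown, with p the proportional difference.

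- Percent change over CV: d = p / CV
- Log-scale increase: d = ln(1 + p) / s
- Log-scale decrease: d = −ln(1 − p) / s

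Here s = √ln(1 + CV²), which is 0.2462 at CV 0.25 and 0.3853 at CV 0.4. For example, 10% at CV 0.25 gives 0.10/0.25 = 0.400, 0.0953/0.2462 = 0.387 and 0.1054/0.2462 = 0.428. All are well below 0.597.

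**Step 3. Power with 45 per group, against the stated 80%.**

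| Difference | CV | Percent change/CV | Log increase | Log decrease |
|---|---|---|---|---|
| 10% | 0.25 | 46.7% | 44.3% | 51.9% |
| 10% | 0.4 | 21.7% | 21.3% | 25.0% |
| 20% | 0.25 | 96.4% | 93.5% | 98.9% |
| 20% | 0.4 | 65.0% | 60.3% | 77.6% |

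**Step 4. What would make each end true.**

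| Quantity | Percent change/CV | Log increase | Log decrease |
|---|---|---|---|
| Largest CV giving 80% power for 10% | 0.167 | 0.161 | 0.178 |
| Largest CV giving 80% power for 20% | 0.335 | 0.313 | 0.387 |
| n per group for 10% at CV 0.25 | 100 | 106 | 87 |
| n per group for 20% at CV 0.4 | 64 | 72 | 48 |

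**Step 5. Difference actually detectable with 80% power at 45 per group.** The formulas are d × CV, exp(d × s) − 1 and 1 − exp(−d × s).

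| CV | Percent change/CV | Log increase | Log decrease |
|---|---|---|---|
| 0.25 | 14.9% | 15.8% | 13.7% |
| 0.4 | 23.9% | 25.9% | 20.6% |

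**Other variants.** Using the CV directly as the log-scale SD gives 43% or 51% for 10% at CV 0.25, and 57% or 74% for 20% at CV 0.4 (increase, decrease). The normal approximation raises the best 10% figure only to 53%. Even a one-sided test reaches only 64% to 65%.

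A 10% figure does appear for a log decrease at CV 0.25 if a one-sample formula is used with n = 45 (power 80.2%), or with 90 per group (81.5%). Neither is the stated design. Both give well over 80% for 20% at CV 0.4 (87% to 97%), so neither explains the whole range.

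**The case against.** The 10% arithmetic is hard to dispute, but four points can be made in the protocol's favour.

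- **The study is exploratory.** Section 12.2 says so, and says that the group difference is unknown. The 10% to 20% is therefore a statement of sensitivity, not a target that set the sample size. This stands and limits the consequence. It does not make the figure right.
- **The 20% end is nearly right on one reading.** Sections 12.2 and 12.4 use the log scale and no direction is given. A log-scale decrease at CV 0.4 has 77.6% power and a detectable difference of 20.6%. This stands. The shortfalls to 60% and 65% depend on the reading and on pairing 20% with CV 0.4, which the text does not state. However, section 3.2 reports larger antibody responses to the recombinant vaccine than to the egg-grown vaccine, so an increase is at least as natural a reading, and it is the least favourable of the three.
- **More than 45 per group may be analysed.** Section 6 allows up to 500 subjects. If these were spread evenly over four arms (125 each, an assumption the documents do not support), power for 10% would be 86% to 92% at CV 0.25 but only 50% to 58% at CV 0.4. The cap is not linked to the power statement, and the documents do not say how it divides or whether it counts re-enrolments. So the miss rates given here are conditional on 45 analysed per group.
- **A mixed-scale reading exists.** If the percent change applied to the mean log count while the CV described raw counts, 10% could reach 80% power at CV 0.25, given a mean natural-log count of about 1.47. The protocol gives no mean count, and this reading switches scale within one calculation.

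**Conclusion.** The concern holds. On every coherent reading of section 12.2, the claim of 80% power for a 10% difference is wrong: power is 44% to 52% at CV 0.25 and 21% to 25% at CV 0.4. This needs no assumption about which CV goes with which difference, because it fails at the most favourable CV. With 45 analysed per group, a true 10% difference would be missed about half the time at CV 0.25 and three times in four or more at CV 0.4.

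The 20% end is weaker ground. It is comfortably met at CV 0.25. At CV 0.4 it falls short by 15 to 20 percentage points on two readings and by about 2 points for a log-scale decrease. Read loosely as a range of detectable differences, both ends are still optimistic: the inputs support about 14% to 16% at the lower end and 21% to 26% at the upper.

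These figures assume no dropout and no multiplicity adjustment. Section 12.2 allows for neither. Section 6.3 does not replace vaccinated withdrawals, and section 12.4 leaves a Bonferroni correction open. Losses or a correction would lower power further.

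**What to change.** Replace the power sentence in section 12.2 with one that follows from its own inputs, for example:

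> For one pairwise comparison at an unadjusted two-sided 0.05, 45 analysed subjects per group provide 80% power to detect, on the log scale, an increase of 16% (CV 0.25) to 26% (CV 0.4), or a decrease of 14% to 21%, relative to the egg-derived group.

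If the sponsor intends a single direction, only that range need be kept. If percent change divided by CV is preferred to the log scale, the range is about 15% to 24%. Either way, the sentence should name the scale, the direction and the CV that goes with each end.

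The cost is one sentence and a less favourable stated sensitivity. Enrolment, endpoints and the analysis do not change.

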12.3 Planned Interim Analyses (if applicable)

No formal interim analysis is planned.

12.3.1 Safety Review

NA, no interim analysis of safety is planned.

12.3.2 Immunogenicity or Efficacy Review

NA, no interim analysis of efficacy is planned. Immunogenicity analysis will be done yearly as part of the overall analysis plan.

12.4 Final Analysis Plan

We will define the groups as: G1 (egg derived vaccine) = G1a (seronegative to pH1N1 virus and receiving egg derived vaccine) + G1b (seropositive and receiving egg derived vaccine); G2 (baculovirus derived vaccine) = G2a (seronegative to to pH1N1 virus and receiving baculovirus derived vaccine) + G2b (seropositive and receiving baculovirus derived vaccine). The log transformation will be applied to stabilize variance, as suggested by our past experience [18]. The between-group and among-group comparison in each of the outcomes will be based on both standard statistical analysis approaches using summary statistics and the complicated random variance model approach. Specifically, each of CD4 specific cells for different Influenza proteins (eg HA, NP etc), memory B cell derived polyclonal antibodies, HAI and MN titers among the four groups and between G1 and G2, between G1a and G2a, and between G1b and G2b, we will use maximum responses or maximum boost responses (maximum value after day 0 – value at day 0) or maximum fold increase as endpoint and do group comparison by ANOVA for among-group comparison and two-sample t-test for between-group comparison, or their nonparametric analogy of Kruskal-Wallis test and Wilcoxon Rank sum test, respectively, may also be applied for robustness. Multiple comparisons may subject to Bonferroni correction, if appropriate. Correlation test such as Pearson correlation analysis, or its nonparametric analogy of Spearman correlation analysis, will be used to study how baseline CD4 responses and/or memory B cell derived polyclonal antibodies, HAI, MN titers affect the boost responses of CD4, memory B cell derived polyclonal antibodies, HAI and MN titers after vaccination.

Various parametric or nonparametric mixed-effects regression approaches will be used to study the dynamic curve of each outcome, to take account of the correlation among observations from the same subjects over time. Group indicator will enter the model as a predictor and thus can be compared simultaneous at each time point and also by difference from difference approach to control the effect of baseline values. Demographic information may be controlled by entering the model as predictors. To further investigate the effect of CD4 cell specificity in helping neutralizing antibody responses, regression analysis will be applied, with boost or fold increase of HAI or MN titers as responses, all the CD4 cell specificities as predictor, possibly adjusting demographic variables. Type I and III sum of squares and standard coefficient estimates can be used to compare the effect of CD4 specificities in helping neutralizing antibody responses. The parametric or nonparametric mixed-effects regression approaches may also be used to compare the effects to take account of within-subject correlation. Among-group plasmablast comparisons will be proceeded by: 1). One-way ANOVA, or its nonparametric analog of Kruskal-Wallis test; 2). Repeated ANOVA or its nonparametric analog of Friedman test for simultaneous pairwise comparison, with within-subject correlation taken into account.

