3.2 Preliminary Data

We have previously demonstrated a wide breadth of CD4 repertoire to influenza, which includes up to 100 distinct peptide specificities in the primary response [6-8]. However, different populations of CD4 T cells, distinguished by their antigen specificity, may not contribute to the all functions important in development of a specific immune response. In particular, it has been demonstrated that protein vaccines and some enveloped viruses [9], delivery of help for antibody responses requires that the B cell and CD4 T cell recognize the epitopes from the

same protein antigen. In the case of influenza antibodies specific for HA and NA, CD4 T cells specific for epitopes in these proteins may be the only ones relevant for development of the antibody response. This help for high affinity Ab production may be primarily provided by cells belonging to the Tfh lineage (reviewed in [10]). However, most studies of the cellular immune response to influenza vaccine have not separately tracked the specific CD4 cells with these combined properties, leaving the contribution of these cells undetected. In contrast, monitoring CD4 T cells that do not have these specificities or function will likely contribute noise to the assessment of CD4 help for Ab responses to influenza.

In the first full year of this study, we found that there were unexpected differences in the serum antibody responses to vaccination between the study groups. In particular, serum HAI antibody responses to the baculovirus-expressed HA were more frequent and the mean fold rise was greater than those to the egg-grown vaccine, possibly consistent with the hypothesis that a more directed CD4 T cell response is more effective at providing help for antibody.

[figure not shown]

Interpretation of these results is complicated by the fact that the dosage level of the rHA vaccine was approximately 3 times that of the egg or cell culture vaccines, so that the more vigorous antibody responses may simply be dose related rather than reflective of CD4 specificity. Despite randomization, pre-vaccination titers were highest in the Fluzone group, as well as history of prior vaccination (18/22 in Fluzone, 16/22 in Flublok, and 13/26 in Flucelvax). In addition, we were unable to find significant numbers of subjects with pre-vaccination serum antibody titers of $\leq 1:8$ to the pH1N1 component of the vaccines.

For these reasons, we modified our protocol by :

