1. Adding the high dose influenza vaccine (Fluzone HD). This may allow separation of the effects of dose from the effects of vaccine composition
2. Eliminating screening for low titers of antibody to pH1N1 and instead stratifying randomization based on history of prior vaccination
3. Continuing to encourage re-enrollment in subsequent years with assignment to the same group, in order to assess the effect of vaccine composition on the response to revaccination.

Secondly, in the 2017-2018 we noted that the Flucelvax H3 component was as poorly immunogenic as that of Fluzone SD despite the differences in manufacturing (cell-based derivation versus egg-based). Post-vaccination antibody titers in Flucelvax recipients were low to all H3N2 viruses tested, including the egg-based, cell-based and two wild-type H3N2 strains. Recent findings have demonstrated that egg adaptation of vaccine viruses during vaccine development for products made in eggs has led to decreased protection against wild-type H3N2 viruses for products like Fluzone SD. However, we would have expected Flucelvax which avoids issues of egg adaptation, since vaccine viruses are grown in cell culture, to be more immunogenic to wild-type H3N2 strains. The reason for our findings of poor immunogenicity of the Flucelvax H3 components which was similar to egg-based Fluzone SD remains unclear and further study is needed outside the scope of the current project.

For this reason, though we have now chosen to eliminate the Flucelvax arm of the study for newly enrolled subjects. However, to preserve the ability to assess the secondary aim of the effect of repeated vaccination without introducing confounders, subjects who have received 2 or more consecutive years of Flucelvax will continue to receive the same vaccine in subsequent years.

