5 STUDY DESIGN

Subjects age 18-49 years will be stratified by their prior vaccination history, followed by randomized assignment to receive one of three licensed vaccines: Fluzone SD, Fluzone HD and Flublok. Block randomization will be performed separately for the two groups. Study subjects who participated in a previous year can be re-enrolled and receive the same vaccine as previously (Fluzone SD, Fluzone HD, Flublok, Flucelvax). Because the goal of the protocol is to evaluate the immune response to the vaccine and is not intended as a formal comparison of the adverse event profile, the vaccine assignment is not blinded. Following vaccination, subjects will have blood sample obtained at the time points illustrated above. The last study visit will take place 6 months after vaccination.

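### Section 12.4 was not updated to the current arms: Fluzone HD has no contrast of its own, Flucelvax has no group, and the randomisation stratum is in no model

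*Combined protocol and SAP*

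**What the plan says.** **Analysis groups (Section 12.4).** The plan sets "G1 (egg derived vaccine) = G1a (seronegative to pH1N1 virus and receiving egg derived vaccine") plus a seropositive G1b, and defines G2 the same way for baculovirus-derived vaccine. The named tests are among the four cells G1a, G1b, G2a and G2b, then G1 vs G2, G1a vs G2a and G1b vs G2b. The mixed models use a group indicator, control baseline by differencing, and may include demographics.

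**Current design (Section 5).** New participants get "randomized assignment to receive one of three licensed vaccines: Fluzone SD, Fluzone HD and Flublok", after stratification by prior vaccination history. "Block randomization will be performed separately for the two groups". Returning participants keep their earlier vaccine, which may be Flucelvax, and are not re-randomised.

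**Why the design changed (Section 3.2).** After the first full year the protocol warned that the "more vigorous antibody responses may simply be dose related rather than reflective of CD4 specificity". It then added Fluzone HD: "This may allow separation of the effects of dose from the effects of vaccine composition". It also changed the stratification: "Eliminating screening for low titers of antibody to pH1N1 and instead stratifying randomization based on history of prior vaccination". Later it chose to "eliminate the Flucelvax arm of the study for newly enrolled subjects".

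**Objectives and hypothesis.** Both primary objectives in Section 4.1 name cell-derived vaccine. The hypothesis in Section 12.1 is narrower: egg-derived versus recombinant.

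**The concern.** The analysis section appears to predate the design changes described in Section 3.2. Three things are at stake.

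- **Dose versus composition.** Flublok carries 45 ug per HA and Fluzone SD 15 ug. HD, at 60 ug, was added because the first-year Flublok advantage could be a dose effect. No named comparison isolates HD.
- **Cell-derived vaccine.** Part of both primary objectives has no named analysis.
- **The stratum.** Randomisation is blocked within prior-vaccination strata, but no model contains that factor.

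The study is open label and its immunogenicity data are analysed yearly (Section 12.3.2). Contrasts not named in advance will be chosen by people who have seen earlier seasons.

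**Working it through.** **1. Design against analysis**

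| Element | Design (Sections 3.2, 4.1, 5, 7.1) | Section 12.4 |
|---|---|---|
| Fluzone SD | randomised arm, egg, 15 ug | in G1 |
| Fluzone HD | randomised arm, egg, 60 ug | in G1 by the egg label, or no group if G1 means SD only |
| Flublok | randomised arm, 45 ug | G2 |
| Flucelvax | arm in the first full year (26 participants); some returning participants continue | no group |
| Randomisation stratum | prior vaccination | not named |
| Subgroup factor | pH1N1 titre screening dropped | pH1N1 serostatus |
| Returning years | not re-randomised | no rule separating them from first enrolments; no rule on combining seasons |

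Both readings of G1 give the same result for HD: there is no SD vs HD test and no Flublok vs HD test.

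**2. The plan's own figure**

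Section 12.2 gives 45 per group, a two-sided 0.05 t test, 80% power, CV 0.25 to 0.4, and a detectable difference of 10% to 20% in HA-specific CD4 counts. Solving the noncentral t for 80% power gives d = 0.597 SD. Multiplying by the CV:

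- 0.597 × 0.25 = 14.9%
- 0.597 × 0.4 = 23.9%

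On the log scale, with SD = √ln(1 + CV²), the range is a 13.7% to 20.6% decrease or a 15.8% to 25.9% increase. The 10% end is not reproduced. That is a separate matter. Here d = 0.597 (about 0.60) serves only as a reference gap.

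**3. If SD and HD are pooled**

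Assumptions: equal SD and HD numbers, a Flublok–SD gap of 0.597 SD, and HD at a fraction f of the way from SD to Flublok. The pooled egg mean then lies f/2 of the way, so the expected G1–G2 difference is 0.597 × (1 − f/2). Section 12.2 does not say whether 45 is per vaccine arm (pooled 90 vs 45) or the whole egg group (45 vs 45), so both are shown. The extra variance from mixing two means is ignored; including it lowers these powers by no more than about two points.

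| f | Expected difference | Share of Flublok–SD gap | Power, 90 vs 45 | Power, 45 vs 45 |
|---|---|---|---|---|
| 0 (HD like SD) | 0.597 | 100% | 90% | 80% |
| 0.5 | 0.448 | 75% | 68% | 56% |
| 1 (HD like Flublok) | 0.299 | 50% | 37% | 29% |

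The pooled result can shrink or stay large without showing why. This table does not apply if G1 means SD only.

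**4. Price of separate contrasts**

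With 45 per arm and Bonferroni over three pairs, alpha is 0.05/3 = 0.0167. Power for the 0.597 SD gap falls from 80% to 65%. The gap detectable with 80% power rises to 0.693 SD, which for CD4 counts is 0.693 × 0.25 = 17% to 0.693 × 0.4 = 28%. If 45 is the whole egg group (22 SD, 23 HD), power for Flublok vs SD at 45 vs 22 is about 44%. The percentages apply to CD4 counts only, because the documents give no HAI variance.

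**5. The stratum**

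Section 3.2 reports prior vaccination in 18/22 (82%) Fluzone, 16/22 (73%) Flublok and 13/26 (50%) Flucelvax participants in the first year. Section 3.1 links prior vaccination to higher baseline titres, so baseline differencing picks up part of its effect. The documents give no input for sizing the remainder.

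**The case against.** The strongest reply is that G1 vs G2 is exactly the contrast in the Section 12.1 hypothesis, in a study that Section 12.2 describes as exploratory. Dose separation is not a listed objective, and Section 3.2 says only that HD may allow it. Vaccine received and Day 0 sera are recorded, so every vaccine-level contrast can still be computed later. Omitting a stratification factor mainly costs precision and does not invalidate a randomised comparison. Within-subject correlation is modelled, and Section 4.2.2 has a separate successive-year outcome.

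Most of this stands. It limits the harm to interpretation, precision and data-informed choice. It does not supply a named use for HD or a Flucelvax comparison, and the latter belongs to both primary objectives. The group indicator in the mixed models takes its meaning from the G1/G2 definitions, so flexible modelling does not close the gap. The successive-year outcome does not say how re-enrolled years are kept out of the randomised comparison.

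The low-titre cells G1a and G2a can still be formed. If seronegative means the 1:8 cut in Section 1, though, Section 3.2 warns that they may be sparse: "we were unable to find significant numbers of subjects with pre-vaccination serum antibody titers of" 1:8 or below.

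**Conclusion.** The mismatch is real and can be read directly from the text. As written, no named test serves the reason for adding Fluzone HD, the cell-derived part of both primary objectives has no comparison, and the stratum is in no model.

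A reader might infer more than the documents support:

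- **That the plan states SD and HD are pooled.** It does not. Pooling follows from the egg label, but the text may predate HD and mean SD only. The 50% to 100% range and any B/Yamagata effect of pooling hold only if they are pooled.
- **That G1 vs G2 is invalid.** It remains a valid test of the Section 12.1 hypothesis. It simply cannot say whether dose or composition drives a difference.
- **That leaving out the stratum biases the result.** The loss is mainly precision, and baseline differencing recovers part of it.
- **That the powers above forecast this trial.** They rest on an assumed 0.60 SD gap, assumed equal SD and HD numbers and an assumed HD response.

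**What to change.** Rewrite Section 12.4 as follows.

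- Define groups by vaccine: Fluzone SD, Fluzone HD, Flublok, Flucelvax.
- Keep the egg-versus-recombinant comparison and state which Fluzone product or products it contains.
- Add Flublok vs SD, HD vs SD and Flublok vs HD. Either apply the Bonferroni option already in Section 12.4 or label them exploratory.
- Add a Flucelvax comparison limited to seasons in which it was concurrently randomised.
- Put the prior-vaccination stratum in the models, alongside baseline control.
- Base randomised comparisons on randomised first enrolments, within season or adjusted for season. Analyse re-enrolled years separately, under the successive-year outcome in Section 4.2.2.
- Leave HD out of B/Yamagata contrasts in seasons when it lacks that antigen, as in the season tabulated in Section 3.1.
- State that dose separation is only partial: Flublok and HD differ in dose (45 vs 60 ug), and HD is trivalent while SD is quadrivalent.
- Disclose that contrasts added now follow sight of earlier seasons' results.

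Section 12.2 should say whether 45 is per vaccine arm. Separately, Section 1 (titre grouping, four vaccines) and Section 8.2 (randomisation described only for those not vaccinated the year before) must be reconciled with Sections 3.2 and 5.

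The cost is wording and analysis code, with no new participants. The real price is the lower power per contrast shown above and contrasts that are partly informed by data already seen.
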